10.9 Patient reported outcomes

Initial bone-targeted β -emitters were approved for the control of painful bone metastases. Radium-223 dichloride appears to be associated with improved/preserved patient reported outcomes as well. We will assess pain prior to and following treatment with the brief pain inventory (and will also collect pain medication data). We will assess global and prostate cancer specific patient reported outcomes with the FACT-P questionnaire. As with the other correlative studies, we will plan to report results for this individual study as well as across current and prior studies, particularly examining subjects that receive what we believe are efficacious doses.

11. Data Reporting / Regulatory Considerations

11.1. Data Collection

The data collection plan for this study is to utilize REDCap to capture all treatment, toxicity, efficacy, and adverse event data for all enrolled patients.

11.1.1. REDCap

REDCap (Research Electronic Data Capture) is a free data management software system that is fully supported by the Weill-Cornell Medical Center CTSC. It is a tool for the creation of customized, secure data management systems that include Web-based data-entry forms, reporting tools, and a full array of security features including user and group based privileges, authentication using institution LDAP system, with a full audit trail of data manipulation and export procedures. REDCap is maintained on CTSC-owned servers that are backed up nightly and support encrypted (SSL-based) connections. Nationally, the software is developed, enhanced and supported through a multi-institutional consortium led by the Vanderbilt University CTSA.

11.2. Regulatory Considerations

All protocol amendments and consent form modifications will be made by the Principal Investigator. Should an external sponsor be identified, they will have the opportunity to review and approve the changes prior to submission of these changes

to the local IRB and distribution to participating sites.

12. STATISTICAL CONSIDERATIONS

12.1. Study Design/Endpoints

This is a phase 1 study of subjects with documented progressive metastatic CRPC with the primary endpoint of determination of MTD (or recommended phase II dose). In general, if there are sufficient numbers of subjects, descriptive statistics (e.g., number of observations, means, standard deviations, medians, and ranges) will be used to summarize data and selected endpoints may be summarized by dosing regimen. Otherwise, subject listings will be provided. No formal hypothesis testing is planned.

The dose-escalation schedule (using 3+3 modified Fibonacci escalation), definitions of DLT, and determination of MTD are defined above (Section 6.2.10). The design is constructed to reduce the chance of escalating the dose when the probability of DLT is high, and increase the chance of escalating the dose when the probability of DLT is low. The maximum tolerated dose is defined as the highest dose level with an observed incidence of DLT in no more than one out of six patients treated at a particular dose level. The dose escalation scheme provides the following probabilities of escalation based on the true chances of DLT at a specific dose level. One can see that the probability of escalation is high if the toxicity risks are low.

True Probability of Toxicity	0.05	0.10	0.20	0.30	0.40	0.50	0.60
Probability of Escalation	0.97	0.91	0.71	0.49	0.31	0.17	0.08

12.2. Phase II

We will enroll up to 27 subjects into the Phase II portion (including the 3-6 used for establishing the MTD). We will define evaluable patients as patients who met eligibility requirements, have initiated therapy, and were not removed from the study for non-compliance or patient withdrawal.

Sample size recommendations for the two-stage design are determined according to Simon's two-stage minimax design. We project a 30% PSA decline proportion of 35%, below which the regimen will be unacceptable and a 30% PSA decline proportion of 60%, above which the regimen will be considered worthy of further exploration. The null hypothesis that the 30% PSA decline proportion is less than or equal to 35% will be tested against the alternative hypothesis that the 30% PSA decline proportion is greater than or equal to 60%.

The sample size computations were performed assuming a 0.10 one-sided level of significance and 90% power assuming a historical control value for PSA decline of 35% and the alternative hypothesis of 60%. If 6 or fewer of the first 16 evaluable patients do not experience a 30% decline in PSA (stage 1), the study will be terminated and declared to have a negative result. If 7 or more patients out of the first 16 evaluable patients experience a 30% decline in PSA, ongoing accrual will proceed to the target sample size of 27 patients (stage 2). The new regimen will be declared active in this patient population and worthy of further testing if 13 or more patients experience a 30% PSA decline among the 27 patients entered. This two-stage design yields a 0.90 probability of a positive result if the true 30% PSA decline proportion is 60%. It yields a 0.90 probability of a negative result if the true 30% PSA decline proportion is 35%. An exact 95% binomial confidence interval will be constructed for the proportion of patients with PSA decline.

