Study Design: Phase I dose escalation study with ^{177}Lu -PSMA-617 using dose fractionation regimen will be performed in patients with documented progressive metastatic CRPC. The cumulative ^{177}Lu dose [**100 mCi (3.7 GBq) – 600 mCi (22.2 GBq)**] will be escalated in up to 6 different dose levels (3 + 3 study design). Additional 10-21 subjects will be enrolled at the MTD/RP2D level in 2-stage design to further assess safety and tolerability and to obtain a preliminary assessment of efficacy.

Study Duration: Primary treatment phase is approximately 3 months after screening

Study Agent/

Intervention Description:

- 1) ^{177}Lu -PSMA-617 [50mCi (1.85GBq) - 300mCi (11.1GBq)] intravenous X2 doses, 2 weeks apart (Visit 1 and 3)
- 2) ^{68}Ga -PSMA-HBED-CC [$5 \pm 2\text{mCi}$ or $185 \pm 74\text{MBq}$] intravenous during screening and at 12 weeks (± 1 week) with standard imaging

Primary Objective:

- Determine the dose limiting toxicity (DLT) of fractionated dose of ^{177}Lu -PSMA-617 (phase I)
- Determine the maximal tolerated and recommended phase II dose of ^{177}Lu -PSMA-617 in a 2-week dose-fractionation regimen (phase I)
- To assess the proportion with PSA decline following treatment with the RP2D of fractionated dose ^{177}Lu -PSMA-617 (Phase II)

Secondary Objectives:

- To assess the rate of PSA decline following fractionated ¹⁷⁷Lu-PSMA-617
 - To assess radiographic response rate by RECIST 1.1 with PCWG3 modifications
 - To assess biochemical and radiographic progression-free survival by PCWG3 criteria
 - To assess overall survival following fractionated ¹⁷⁷Lu-PSMA-617
 - To assess safety of fractionated ¹⁷⁷Lu-PSMA-617 as assessed by CTCAE 4.0
 - To assess changes in CTC count as measured by CellSearch and the rate of favorable CTC count and LDH at 12 weeks following fractionated ¹⁷⁷Lu-PSMA-617
 - To examine whole body distribution of ¹⁷⁷Lu-PSMA-617
 - Estimate radiation dosimetry of ¹⁷⁷Lu-PSMA-617 and correlate toxicity with radiation dosimetry

Exploratory Objectives:

- Disease assessment with ⁶⁸Ga-PSMA-HBED-CC PET/CT prior to and following investigational treatment
- To assess genomic DNA repair pathways in relationship to outcome following fractionated dose ¹⁷⁷Lu-PSMA-617
- To assess patient reported outcomes using FACT-P and the Brief Pain Inventory short form
- To assess the immune effect of ¹⁷⁷Lu-PSMA-617
- To assess reproducibility of ⁶⁸Ga-PSMA-HBED-CC PET/CT

Endpoints:

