As there is a reasonably large pool of short- and long-term experience with PSMA-directed 177Lu, we will transition to a phase II cohort will be enrolled at the MTD/RP2D to gain additional safety data as well as preliminary efficacy data. We will enroll up to 27 subjects in the Phase II trial utilizing a Simon two-stage design (including the 3-6 patients used for establishing the MTD). For the phase II portion, we will define evaluable patients as those who met eligibility requirements, have initiated therapy, and were not removed from the study for non-compliance or withdrawal. Sample size recommendations for the two-stage design are determined according to Simons two-stage minimax design. The first stage will accrue a total of 16 patients (including those who were treated at the MTD in the phase I portion), if 6 or fewer of the first 16 evaluable patients do not experience a 30% decline in PSA, the study will be terminated and declared to have a negative result. If 7 or more patients out of the first 16 evaluable patients experience a 30% decline in PSA, 9 more patients will be accrued in Stage 2 (total sample size of 27). The new regimen will be declared to have activity and be worthy of further testing if 13 or more patients experience a 30% PSA decline among the 27 patients who are part of the phase II trial.

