6.4. Duration of Therapy and Criteria for Removal from Study

Duration of treatment portion of the study (excluding screening time) will be approximately 85 Days (± 7 days). By signing the informed consent form and agreeing to participate in this study, the subjects are required to participate in entirety up to the completion of all scheduled visits and study procedures, or until one of the following criteria applies:

- A protocol violation occurs
- Disease progression occurs
- A serious or intolerable adverse event occurs (that in the opinion of the Investigator, requires the subject's discontinuation)
- The Investigator withdraws the subject (at the Investigator's discretion for reasons other than the adverse event)
- The Principle Investigator terminates the protocol
- The subject requests to be discontinued from the protocol
- The subject is lost to follow-up
- Intercurrent illness that prevents administration of ⁶⁸Ga-PSMA-HBED-CC or ¹⁷⁷Lu- PSMA-617
- Previous anaphylactic reaction to PSMA peptides/ligands

The investigators or physicians may stop the protocol or terminate a subject's participation in the protocol at any time should they judge:

- That it is not in the subject's best interest to continue
- If the subject experiences a protocol-related injury
- If the subject needs life-saving medications/procedures/treatment
- If the subject does not comply with the study plan
- General or specific changes in the patient's condition render the patient unacceptable for further treatment in the judgment of the investigator

They may also remove the subject from the study for various other administrative and medical reasons. They can do this without the patient's consent.

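### The phase II PSA analysis drops treated patients removed for non-compliance or withdrawal even when their PSA outcome is known, so the reported rate describes those who stayed and complied

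*Combined protocol and SAP*

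**What the plan says.** - **Objective.** The Protocol Summary gives the phase II primary objective as "To assess the proportion with PSA decline following treatment with the RP2D". It does not condition on what happens after treatment.
- **Who counts.** Section 12.2 defines evaluable patients as those who met eligibility, "have initiated therapy, and were not removed from the study for non-compliance or patient withdrawal". Section 4.2 has nearly the same rule, "have initiated therapy, and were not removed from the study for non-compliance or withdrawal", without the word patient. Neither sets a time limit or an exception for a man whose PSA outcome is known.
- **Decision rule.** Stage 1 is judged on the first 16 evaluable patients and needs at least 7 with a 30% decline. The final rule needs 13, counted in 12.2 over the 27 who enter and in 4.2 over the 27 who form the phase II trial. Phase II enrolment is capped at 27.
- **Removal.** Section 6.4 lists progression, serious or intolerable adverse event, protocol violation, loss to follow-up and intercurrent illness. It also lists "The Investigator withdraws the subject (at the Investigator's discretion for reasons other than the adverse event" and, among the grounds for ending participation, "If the subject does not comply with the study plan".
- **PSA visits.** The trial is open-label, and PSA is measured on Days 1, 15, 29, 57 and 85.
- **A second definition.** Section 12.7.2 requires completed treatment plus at least 12 weeks of follow-up, and leaves open whether non-evaluable patients are replaced.
- No all-treated or sensitivity analysis of the PSA proportion is specified.

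**The concern.** The rule selects on an event after treatment, and that event can depend on the outcome. A man whose PSA has not fallen by Day 57 has a reason to withdraw. An investigator who judges non-compliance has seen the same PSA values. In either case a known non-response leaves the denominator. The quantity estimated is then decline among those who stayed and complied, not decline following treatment.

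Two results are exposed: the stage 1 gate, which explicitly counts evaluable patients, and the reported proportion with its exact confidence interval. In a single-arm trial that one proportion carries the efficacy conclusion.

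**Working it through.** **Inputs.** From Section 12.2: null rate 0.35 and alternative 0.60 ("historical control value for PSA decline of 35% and the alternative hypothesis of 60"%), planned "assuming a 0.10 one-sided level of significance and 90% power", n1 = 16 with at least 7 responders to continue, n = 27 with at least 13 to declare activity. I take stage 2 as 27 − 16 = 11 patients and read the stopping rule as 6 or fewer responders. Removal rates are not in the documents and are assumed.

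**Step 1: reproduce the plan.**
P(active | p) = Σ over x = 7 to 16 of Bin(x; 16, p) × P(Bin(11, p) ≥ 13 − x).
This gives 0.0979 at p = 0.35 and 0.9001 at p = 0.60, so the stated 0.10 and 0.90 hold when the denominator does not depend on outcome.

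**Step 2: bias in the evaluable-set rate.** Let w be the share of treated patients excluded. If all of them are non-responders and the true rate is 0.35, the evaluable rate is q = 0.35/(1 − w). At w = 5%, 0.35/0.95 = 0.368. The chance of passing stage 1 is P(Bin(16, q) ≥ 7).

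**Step 3: type I error under two readings of the final denominator.**
(a) Excluded men are replaced until 16 and then 27 are evaluable: evaluate the Step 1 formula at q.
(b) 27 are entered, with no replacement beyond 27 and the threshold of 13 kept: a dropped non-responder still uses one of the 27 places, so only the stage 1 gate moves (simulation, 400,000 runs or more).

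| w | q | P(pass stage 1) | (a) replaced | (b) cap of 27 |
|---|---|---|---|---|
| 0% | 0.350 | 0.312 | 0.098 | 0.098 |
| 2% | 0.357 | 0.334 | 0.112 | 0.100 |
| 5% | 0.368 | 0.370 | 0.137 | 0.102 |
| 10% | 0.389 | 0.436 | 0.191 | 0.105 |
| 15% | 0.412 | 0.512 | 0.264 | 0.108 |

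The stage 1 column applies the binomial formula at q. Reading (b) is bounded by dropping the gate altogether: P(Bin(27, 0.35) ≥ 13) = 0.1106.

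**Step 4: milder and neutral cases.** If those excluded respond at half the rate of the others, q = 0.35/(1 − w/2). Under reading (a) this gives 0.137 at w = 10% and 0.162 at w = 15%. If 10% of responders and 10% of non-responders are dropped, q stays at 0.35. Type I error is then 0.098 under (a). Under (b), with dropped responders not counted, it is a conservative 0.049, and power falls to 0.781.

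**The case against.** The strongest objection is that the type I error hardly moves under the plan's wording. Section 12.2 caps enrolment at 27 and applies the 13-responder threshold to the patients entered; only stage 1 is tied to evaluable patients. A reader might infer from column (a) that the plan runs a false-positive risk of 0.19 or 0.26. The documents do not support that: 12.7.2 leaves replacement open and does not promise it, and under the cap the ceiling is 0.111. This part of the objection stands.

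A reader might also infer that every man taken off with a rising PSA disappears. He does not. Progression and adverse events are separate removal reasons in 6.4, and neither definition of evaluable names them. Protocol violation is not named either. Section 12.2 limits withdrawal to the patient's own, so a withdrawal by the investigator is clearly excluded only if the broader word in 4.2 governs. The investigator's part in the exclusion is therefore certain only for non-compliance.

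Third, treatment is two infusions two weeks apart, which limits the scope for non-compliance with treatment. The high end of the range is extreme: w = 15% with all exclusions non-responders means 0.15/0.65 = 23% of non-responders dropped and no responders.

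What survives is narrower. The definition excludes men with known outcomes, stage 1 uses it directly, and a rate reported on the evaluable set carries the Step 2 bias under either reading.

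**Conclusion.** The concern holds as a mismatch between the objective and the analysis set, with a possible upward bias in the reported rate and an easier stage 1 gate. The bias is 1.8 percentage points (35% to 36.8%) if 5% of treated patients are excluded and all are non-responders. It is 3.9 points at 10%.

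Material inflation of type I error is conditional. It needs exclusion to be more frequent among non-responders and excluded men to be replaced until 27 are evaluable. Under the cap of 27 entered it is about 0.100 to 0.108 over the assumed range. All these sizes rest on assumed removal rates. The plan should be changed because the rule lets outcome affect the denominator and the correction is wording only; nothing in the documents shows that such removals are frequent.

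**What to change.** 1. In 4.2 and 12.2, delete the exclusion for non-compliance or withdrawal.
2. Use one denominator for stage 1, the final rule and the confidence interval: all eligible patients who received at least one 177Lu-PSMA-617 infusion at the RP2D.
3. Classify each man on PSA observed up to leaving. A qualifying decline is a response; no qualifying decline is a non-response.
4. Make 12.7.2 consistent for the PSA endpoint. Otherwise its requirement of completed treatment plus 12 weeks would still exclude early leavers.
5. Report the present evaluable-set rate as a sensitivity analysis.

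**Cost.** No extra patients are required and type I error does not rise. The estimate becomes slightly conservative. If all leavers count as non-responders and the 60% alternative applies only to men who stay, the response rate is 0.60 × (1 − share leaving). Power then falls from 0.900 to 0.877, 0.836 or 0.750 at 2, 5 or 10% leaving. If losses near the upper end are expected, a small allowance in the sample size should be considered. The loss is smaller where leavers have already shown a qualifying decline, because those men count as responders.

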12.3. Sample Size/Accrual Rate

The planned sample size for this dose escalation Phase I study is between 6-36 and between 16-27 for phase II. The accrual rate is anticipated to be 1-2 patients/month on average (with expected pauses between dose-escalation cohorts and between stage 1 and stage 2 of the phase II trial).

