12.4. Stratification Factors

This is not a randomized trial and there are no planned stratification factors. Descriptive statistics will be utilized. Stopping rules for futility are in place as per Section 4.2.

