12.6. Interim Analysis

No interim analysis is planned (though safety analyses will occur in real-time and prior to each dose-escalation). During phase II, ongoing analysis during Step 1 will determine whether or not to proceed to step 2.

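### The stage 1 futility rule is inverted in sections 4.2 and 12.2: as worded, it ends phase II as negative at 10 or more responders of 16

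*Combined protocol and SAP*

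**What the plan says.** Section 12.2 specifies a Simon two-stage minimax design for the phase II endpoint, a 30% PSA decline. The null proportion is 35%, the alternative 60%, the one-sided level 0.10 and the power 90%. Stage 1 has 16 evaluable patients, the total is 27, and activity is declared at 13 or more responders.

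The study is to be terminated and declared negative "If 6 or fewer of the first 16 evaluable patients do not experience a 30% decline in PSA (stage 1"). The next sentence starts "If 7 or more patients out of the first 16 evaluable patients experience a 30% decline in PSA" and continues accrual to 27. Section 12.2 then claims: "This two-stage design yields a 0.90 probability of a positive result if the true 30% PSA decline proportion is 60"%, with the same 0.90 probability of a negative result at 35%.

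Section 4.2 has the same stopping sentence: "if 6 or fewer of the first 16 evaluable patients do not experience a 30% decline in PSA, the study will be terminated". On 7 or more responders it adds that "9 more patients will be accrued in Stage 2 (total sample size of 27").

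Three later sections touch on the decision without giving a threshold:

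- Section 12.3 sets the size at "between 16-27 for phase II".
- Section 12.4 says "Stopping rules for futility are in place as per Section 4.2".
- Section 12.6 says "ongoing analysis during Step 1 will determine whether or not to proceed to step 2".

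**The concern.** The stopping sentence counts patients who fail to respond, while the cut-off of 6 belongs to patients who do respond. Taken at its word, it calls the trial negative for a high response count and says nothing about a low one. The following sentence in each section says the opposite for the same high counts.

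No other text repairs this. Section 12.4 sends the reader to section 4.2 for the futility rule, and section 4.2 carries the same inverted wording, so checking one section against the other confirms the error.

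This is the go/no-go rule for the phase II primary objective. The cover page lists three participating sites, and section 14 has a DSMB that decides on continuation. They should be able to apply the rule as written. If the drug is inactive (true proportion 35%), a stage 1 stop is the most likely outcome under the intended rule, so the misworded sentence governs the case that matters most for patients.

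**Working it through.** **Inputs (section 12.2).** p0 = 0.35, p1 = 0.60, n1 = 16, n = 27, active if total responders ≥ 13, one-sided level 0.10, power 0.90. Let X be the number of responders among the first 16.

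**Step 1: translate the wording.** Six or fewer non-responders means 16 − X ≤ 6, so X ≥ 10.

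| Responders of 16 | Termination sentence, literally | Proceed sentence |
|---|---|---|
| 0–6 | does not apply | does not apply |
| 7–9 | does not apply | go to stage 2 |
| 10–16 | stop, negative | go to stage 2 |

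**Step 2: reproduce the plan's own figures.** For a set C of stage 1 counts that continue,

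P(active | p) = Σ over x in C of P(X = x) × P(Y ≥ 13 − x), with X ~ Bin(16, p) and Y ~ Bin(11, p).

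With the stop at 6 or fewer responders, C = {7,…,16}. This gives power 0.9001 at 60% and type I error 0.0979 at 35%, so the probability of a negative result at 35% is 1 − 0.0979 = 0.9021. Both agree with the stated 0.90.

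An exhaustive search over two-stage designs with totals from 15 to 35 (type I error ≤ 0.10, power ≥ 0.90) finds 27 as the smallest feasible total. Among designs of that size, the one with the lowest expected sample size at 35% stops at ≤ 6 of 16 and rejects the drug at ≤ 12 of 27. That is the stated minimax design with 'do not' removed.

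**Step 3: stage 1 probabilities.**

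| | p = 0.35 | p = 0.60 |
|---|---|---|
| P(X ≤ 6) | 0.688 | 0.058 |
| P(7 ≤ X ≤ 9) | 0.289 | 0.415 |
| P(X ≥ 10) | 0.023 | 0.527 |

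Expected sample size at 35% under the intended rule: 16 + 11 × (1 − 0.688) = 19.4.

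**Step 4: operating characteristics under each reading.**

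| Rule applied | Type I error (35%) | Power (60%) |
|---|---|---|
| Intended: stop at 0–6, n = 27 | 0.098 | 0.900 |
| No stage 1 stop, n = 27 | 0.111 | 0.926 |
| Literal stop at 10–16; 0–6 also stop | 0.079 | 0.374 |
| Literal stop at 10–16; 0–9 continue | 0.091 | 0.400 |
| Stop at 0–6, but 9 added (n = 25), cut-off 13 | 0.058 | 0.836 |

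Without a stage 1 stop, every trial treats 27 patients. At a true 35% that is 27 − 19.4 = 7.6 more on average than intended.

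**Step 5: the stage 2 count in section 4.2.** 16 + 9 = 25, whereas 27 − 16 = 11. The last row of the table shows the result if 9 were enrolled and the cut-off of 13 kept.

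**The case against.** The strongest reply is that this is a slip nobody would follow. The proceed sentence is explicit and correct in both sections, and its complement is 0 to 6, the same 6 that appears in the faulty sentence. The named design and its parameters lead to exactly those boundaries. The size of 16 to 27, the reference to futility rules and the stage 1 decision in section 12.6 all fit a stop at 6 or fewer responders. So does the Protocol Summary's figure of 10 to 21 additional patients (16 − 6 and 27 − 6), provided six patients carry over from phase I; the plan allows 3 to 6. No other reading fits.

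That is right about the intent, and it limits the consequence. The powers of 0.37 and 0.40 require someone to obey one sentence and ignore the next. The case with no stop conflicts with sections 12.3, 12.4 and 12.6. Both are hypothetical. The 9-for-11 slip is a separate arithmetic error that occurs only in section 4.2, whose own stated total is 27; section 12.2, where the error rates are claimed, does not contain it. The documents also do not show whether the stage 1 decision is still to come.

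The reply does not remove the error. A pre-specified stopping rule should be stated correctly somewhere, and here both statements of it are wrong in the same way.

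**Conclusion.** The concern holds. The stage 1 stopping sentence is inverted in both places where it appears, it contradicts the sentence after it for 10 to 16 responders, and the stop at 0 to 6 responders is nowhere stated. At a true 60%, the literal condition would be met with probability 0.527.

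The defect is in the wording. With the stop at 6 or fewer responders of 16 and a total of 27, the design delivers its stated properties: type I error 0.098, power 0.900, and a stage 1 stop with probability 0.69 at 35% and 0.06 at 60%.

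These figures assume independent responses with a common probability and exactly 16 and 27 patients counted at the two looks. Who counts as evaluable is a separate matter and was not examined here. The correction is needed because this is the trial's stated decision rule, not because the worst-case powers are likely to occur.

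**What to change.** - In sections 4.2 and 12.2, delete 'do not' from the stopping sentence, so that the study is terminated and declared negative when 6 or fewer of the first 16 evaluable patients have the 30% PSA decline.
- Keep 7 or more responders as the condition for continuing to 27.
- In section 4.2, change the stage 2 addition from 9 to 11 patients (16 + 11 = 27).
- If the stage 1 decision has already been made, record which rule was applied.

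The cost is two words deleted in two places and one number changed. The cut-offs, total sample size and analysis are unaffected.

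### The planned 95% interval for PSA response takes no account of the two-stage design; a two-stage interval, p-value and estimate should be named (reporting only, low severity)

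*Combined protocol and SAP*

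**What the plan says.** Section 12.2 (Phase II) of the combined protocol and SAP sets the design: "Sample size recommendations for the two-stage design are determined according to Simon's two-stage minimax design". The null rate is 35% and the alternative 60%. The error rates are given as follows: "The sample size computations were performed assuming a 0.10 one-sided level of significance and 90% power".

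The rule is expressed in counts. At stage 1: "If 7 or more patients out of the first 16 evaluable patients experience a 30% decline in PSA, ongoing accrual will proceed". At the end, the regimen is declared active "if 13 or more patients experience a 30% PSA decline among the 27 patients entered".

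The same paragraph closes with the interval: "An exact 95% binomial confidence interval will be constructed for the proportion of patients with PSA decline". It does not mention a two-stage interval, p-value or estimator, and it does not say whether the interval is descriptive or is meant to match the test. Nothing elsewhere supplies this. The efficacy analysis text under section 10.8 plans 95% binomial intervals for other proportions (RECIST, CTC, LDH/CTC), and section 12.5.2 gives only descriptive analysis of PSA response.

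**The concern.** The proportion comes from a design that can stop at 16 patients, so the final count out of 27 is not an ordinary binomial count. A single-stage interval and the raw proportion treat it as one. Two things follow.

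- The nominal 95% level is not guaranteed, and the raw proportion is biased.
- An analyst using ordinary binomial software at 13/27 would get a p-value above 0.10 for a result that the protocol calls positive. The plan has no sentence to prevent that.

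What is at stake is how clearly the primary phase II result is reported. The go/no-go decision is not at stake.

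**Working it through.** **Inputs (section 12.2).** p0 = 0.35, p1 = 0.60; n1 = 16, continue with 7 or more; n = 27, active with 13 or more; one-sided alpha 0.10, power 0.90. Stage 2 is taken as 27 − 16 = 11 patients.

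**1. Reproduce the plan's design.** With X1 ~ Bin(16, p) and X2 ~ Bin(11, p),

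P(active) = Σ over x1 = 7..16 of P(X1 = x1) · P(X2 ≥ 13 − x1).

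- At p = 0.35: 0.0979. At p = 0.60: 0.9001.
- A full search for the minimax design returns the same rule (stop at 6 or fewer of 16, negative at 12 or fewer of 27).

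The stated error rates are correct.

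**2. P-value at the boundary, 13/27.**

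- Single-stage: P(Bin(27, 0.35) ≥ 13) = 0.111, above 0.10.
- Two-stage: the sum in step 1 at p = 0.35, which is 0.098, below 0.10.

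The two differ because the single-stage tail counts paths to 13 or more that would have been stopped at 16. At 14/27 they are 0.054 and 0.051, so the disagreement is confined to exactly 13 responders. The probability of that outcome is P(≥ 13) − P(≥ 14): 0.0979 − 0.0508 = 0.047 at p = 0.35, and 0.9001 − 0.8419 = 0.058 at p = 0.60.

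**3. Intervals.** Plain limits are Clopper-Pearson. Two-stage limits use the stage-wise (Jennison-Turnbull) ordering, in which every stage 2 result ranks above every stop at stage 1. The lower limit solves P(reach stage 2 and total ≥ s; p) = a/2. The upper limit solves P(stop at stage 1, or total ≤ s; p) = a/2.

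| Responders of 27 | Plain 95% | Two-stage 95% | Plain 80% lower | Two-stage 80% lower |
|---|---|---|---|---|
| 13 (48.1%) | 28.7–68.1% | 29.2–68.8% | 34.5% | 35.1% |
| 14 (51.9%) | 31.95–71.3% | 32.2–71.5% | 38.0% | 38.2% |
| 15 (55.6%) | 35.3–74.5% | 35.4–74.6% | 41.5% | 41.6% |

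The lower limit of a two-sided 80% interval is the one-sided 90% lower bound, which is the level of the test.

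**4. Coverage of the plain 95% interval under this design** (n = 16 if stopped, otherwise 27), on a grid of p:

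- minimum 94.4%, near p = 0.647; 96.8% at p = 0.35 and 96.2% at p = 0.60;
- the upper limit lies below the true rate up to 3.9% of the time (nominal 2.5%);
- the lower limit lies above the true rate no more than 2.5% of the time.

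**5. Point estimate.** The raw proportion has bias −1.8 percentage points at p = 0.35 and −0.6 at p = 0.60. The unbiased estimate (UMVUE) after reaching stage 2 with s responders is

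Σ C(15, x1 − 1)·C(11, s − x1) / Σ C(16, x1)·C(11, s − x1), with x1 from 7 upwards.

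At s = 13 this is 8,415,290 / 16,588,560 = 50.7%, against 13/27 = 48.1%.

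**6. Where the 95% interval includes 35%.** This happens at 13 and 14 responders. The probability of either is 0.155 at p = 0.60 and 0.075 at p = 0.35. The two-stage 95% interval also includes 35% at both counts.

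**The case against.** The strongest reply is that no decision uses the interval. Activity is defined by counts whose exact error rates match the plan, and no rule requires the interval to exclude 35%. A one-sided 0.10 test and a two-sided 95% interval work at different levels and need not agree, and a 95% interval is a common summary beside a screening test. The plain interval does not overstate activity either: its lower limit is valid, and the bias in the raw proportion is downward. The two-stage correction at 13/27 moves the lower limit by only half a point.

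All of this stands. It disposes of a stronger reading that a reader might infer: that declaring activity at 13 or 14 of 27 beside a 95% interval containing 35% is a contradiction in the plan. The documents do not support that. The overlap comes mainly from choosing 95% rather than the level of the test. At 14/27 it comes wholly from that choice, since the plain 80% lower limit is already 38.0%. Changing to a two-stage 95% interval does not remove it.

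What the reply leaves untouched is narrower. The plain method's upper limit misses more often than stated, the raw estimate is biased, and at 13/27 the ordinary p-value and the ordinary bound at the level of the test (34.5%) fall on the wrong side of the plan's own decision.

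**Conclusion.** The point holds as a reporting refinement of low severity. The planned interval and the raw proportion ignore the two-stage design. The cost is at most about 0.6 points of coverage (94.4% against 95%), an upper-limit miss rate of up to 3.9%, and a 2.6-point gap between raw and unbiased estimates at 13/27 (50.7 − 48.1). A single-stage p-value would disagree with the decision at one outcome only, 13/27. The decision rule, its error rates and the sample size are unaffected, and nothing here suggests that the trial could declare activity wrongly more often than planned.

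Three assumptions matter. The phrase exact binomial is read as single-stage Clopper-Pearson, although the text does not say unadjusted. Stage 2 has 11 patients, as the total of 27 in section 12.2 implies; section 4.2 speaks of 9 more, which does not add up to its own total of 27. The stage 1 rule is read as stopping with 6 or fewer responders, as its companion sentence on 7 or more requires. The two-stage limits depend on the stage-wise ordering.

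**What to change.** In section 12.2, replace the interval sentence with wording to this effect:

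- The proportion with a 30% PSA decline will be reported with an exact two-stage 95% confidence interval (stage-wise ordering), the exact two-stage p-value, the two-stage one-sided 90% lower confidence bound and the UMVUE, alongside the raw proportion.
- The decision on activity rests on the responder count. The 95% interval is descriptive and need not exclude 35%.

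At 13/27 the report would then give 13 responders, raw 48.1%, UMVUE 50.7%, two-stage p = 0.098, 90% lower bound 35.1% and 95% interval 29.2% to 68.8%. The p-value and the lower bound agree with the decision, and the label explains why the 95% interval is wider. If the trial stops at stage 1, this ordering gives the same interval as the plain one on 16 patients, so nothing is lost there.

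The cost is a few lines of code and two confidence levels to explain. Sample size, conduct and the decision rule do not change. Fixing the method before analysis also avoids choosing an interval after the count is known.
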